Participants expressing interest in the study that do not meet certain eligibility criteria, e.g. have experienced a change in medication or have been hospitalized within the last 4 weeks, have an upcoming medical procedure, surgery or treatment that would interrupt their participation, have experienced suicidal ideation or behavior within two months or those with known future end dates to psychotherapy treatment, will be placed on hold and re-screened for appropriate eligibility criteria.

Study Procedures/Research

Study Procedures: Participants at the recruitment Site will flow through the study in the following manner:

1. *Informed Consent Discussion:* Site Study personnel will discuss study goals, activities, and requirements with the parent/legal guardian and/or potential participant; complete the informed consent discussion, and if/when appropriate the potential participant will complete assent/consent to join study.
Duration: ~30-60 minutes remotely or in-person at the Study Site.
2. *Initial Screening Visit (V0):* Following assent/consent, Site Study personnel will perform diagnostic assessments and interviews and assess inclusion/exclusion to determine if the participant is eligible for enrollment.
Duration: ~2-3 hours remotely or in-person at the Study Site. The *Informed Consent Discussion* and the *Initial Screening Visit (V0)* may occur independently or may be combined in a single session.
3. *Baseline Assessment (V1):* Following enrollment, the participant will perform all social/cognitive baseline characterization assessments and questionnaires prior to the intervention period. Duration: ~2 hours remotely or in-person at the Study Site.
4. *Randomization:* Participants will be randomized into one of two treatment groups.
5. *Mobile device Set-Up and Proctored Application Use (V2):* The participant will be oriented to the intervention activities and program application(s). Participants assigned to both WASABI and the active control arm will complete a series of mobile assessments during this visit (embedded baseline assessments via BrainHQ) .

Participants with a compatible personal device that are willing to download the necessary application(s) for program use will have their device set-up at this visit. Participants assigned to WASABI will be guided to schedule reminders for

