Standard diagnostic criteria and classifications for Anxiety Disorder as defined by the Mini International Neuropsychiatric Interview for Children and Adolescents (MINI-KID), a brief structured diagnostic interview using DSM-IV criteria and standard diagnostic criteria and classifications for Social Anxiety, as defined by the Social Phobia and Anxiety Inventory-Brief version, as defined by a score of 25 or greater, will be used to assess eligibility. If information is gathered from self-report questionnaires, emergency contacts, the participant's psychiatrist, therapist, and/or primary care physician, this may be used to corroborate and supplement the participant interview to assess eligibility.

Clinical and Neuropsychological assessments and characterization

The study will employ empirically validated assessment measures specific to anxiety and depression, and also adhere to recent *NIH Toolbox* recommendations. Collectively, we have chosen a battery based on five key criteria (when possible), including 1) existing standardization, to ensure reliable data collection procedures, 2) sensitivity to the impairment typical of this study population, 3) normative data availability, 4) reasonable test-retest

stability (i.e., to control for potential participant improvement through strategy learning over repeated measures) for use in a treatment trial with two repeated measures, and 5) good sensitivity to change following remediation. Several measures will be used to provide gross clinical characterization.

Cognitive Assessments

Screening. Cognitive status will be assessed using WASI-II, specifically the Vocabulary and Reasoning subscales. Participants must score $IQ > 80$ to enroll in the study. Adult participants will undergo an additional cognitive assessment, the UBACC. Participants must score within the normal range; participants who cannot pass the UBACC will not be eligible for enrollment.

Anxiety and Social Anxiety

Clinician ratings of anxiety and social anxiety symptoms will be assessed through the Liebowitz Social Anxiety Scale for Children and Adolescents (LSAS-CA).⁵⁰ Self-report inventories of social anxiety symptoms through the Social Phobia and Anxiety Inventory (SPAI)⁵¹ will be completed at the *Baseline* (V1) and *End of Study* (V3). Broad measure anxiety and potential generalization of treatment to other anxiety domains will be captured through the Multidimensional Anxiety Scale for Children 2nd Edition (MASC-2).

Social Functioning

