We will assess social skills by administering the Social Skills Questionnaire (SSQ);⁵² and social functioning using the Adolescent Social Self-Efficacy Scale (ASSES).⁵³

Suicidality Assessment

The Columbia Suicide Severity Rating Scale (C-SSRS) will be used to screen for and assess suicidal ideation. Those that do not meet inclusion criteria for this assessment will not be enrolled in the study. Participants who do not meet this criteria but express interest in the study may be reengaged and reassessed following a 2-month period. The C-SSRS will be repeated at the *End of Study* (V3) Visit to screen for any changes in suicidal ideation over the course of the study. The C-SSRS may be re-administered during the intervention period, as needed, should there be any concerns for safety or increasing symptoms.

Intervention Embedded Assessments

Cognitive Biases. Participants in both the WASABI and active control arm will complete embedded assessments immediately before and after the 12-week intervention. Additionally, for participants assigned to WASABI, during the intervention and program use period, WASABI weekly collects performance data on two cognitive assessments that capture attention bias assessment, and an interpretation bias assessment. Participants assigned to

receive WASABI will also complete a weekly SPAI-B assessment. Performance on these assessments will be modeled longitudinally to examine if these measures can serve as potential moderators and mediators of treatment efficacy.

The primary outcome measures, including assessment adherence, dCBGT and IM engagement, EMA, SPAI-B and overall program completion rates, reported adverse effects, usability ratings and clinician burden, will be used to assess feasibility, acceptability and usability of WASABI.

Secondary outcomes include clinical ratings of anxiety and social anxiety symptoms (LSAS-CA), self-report inventories of social anxiety symptoms (SPAI), broad measures of anxiety (MASC-2), as well as measures that capture social skills (SSQ), and social functioning (ASSEs).

Description of Protocol Devices (Software Program)

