- *Standardized Self-Report Questionnaires.* WASABI includes standardized self-reports of social anxiety (SPAI-B), and weekly assessments that implicitly evaluate core cognitive operations known to be impaired in social anxiety (e.g., attention bias, interpretation bias). The SPAI-B consists of 16 items using a 5-point Likert scale (1–5). It assesses the cognitive, somatic, and behavioral symptoms (triple-response-system) and captures interactional and performance-provoking socially anxious situations. In the attention bias assessment, neutral and negative faces are presented for a limited time, followed by a letter that is displayed in the region of the screen where the neutral face was. Participants need to identify the letter as quickly as possible. In the interpretation bias assessment, a series of ambiguous images is presented for a limited time (for example, a situation in which one friend walks past another without acknowledgement), followed by a screen where three images with clear emotional valence are concurrently presented. Participants need to choose the image that captures the emotion that best explains the ambiguity of the previous images. The rationale behind the assessment is that participants with interpretation bias may develop expectations that ambiguous situations are more likely to end negatively.
- *WASABI Alerts.* If WASABI detects clinically-significant social anxiety through EMA metrics (EMA Thoughts, EMA Feelings, EMA Goals), cognitive biases assessments, and the Social Phobia and Anxiety Inventory-Brief (SPAI-B), the monitoring clinician will receive an alert that cues them to connect via Instant Messaging with the participant. The algorithm will be used to alert the WASABI clinician when a trial participant reaches clinically significant social anxiety, so that symptom exacerbation can be addressed over Instant Messaging.

EMAs, cognitive biases assessments and self-reports are meant to support standard clinical care by providing additional structured tools for an individual to use to address cognitive biases that often co-occur with anxiety. To complete these activities, a participant opens a

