Appendix I. Table of Assessments

Assessment	Screening	V1	V3
Informed Assent/Consent	X		
Demographics	X		
Medical History Questionnaire and Screening	X		
Mini International Neuropsychiatric Interview for Children and Adolescents (MINI-KID)	X		
Social Phobia and Anxiety Inventory-Brief version	X		
Wechsler Abbreviated Scale of Intelligence (WASI-II)	X		
C-SSRS, Baseline	X		
Medications, Baseline	X		
Liebowitz Social Anxiety Scale for Children and Adolescents (LSAS-CA)		X	X
Social Phobia and Anxiety Inventory (SPAI)		X	X
Multidimensional Anxiety Scale for Children 2nd Edition (MASC-2)		X	X
Adolescent Social Self-Efficacy Scale (ASSES)		X	X
Social Skills Questionnaire (SSQ)		X	X
Medications, Since Last Visit		X	X
C-SSRS, Since Last Visit		X	X
Adverse Effects		X	X
Unanticipated Adverse Effects		As needed	
Study Exit		As needed	

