7. Reported side effects (raw score). *Based on our previous findings, we expected 0 adverse events due to program use).*

The secondary outcome measures were collected by trained personnel blind to treatment assignment at baseline and after the intervention:

- clinician ratings of anxiety and social anxiety symptoms through the Liebowitz Social Anxiety Scale for Children and Adolescents (LSAS-CA)
- self-report inventories of social anxiety symptoms through the Social Phobia and Anxiety Inventory-Brief (SPAI-B) – at baseline, weekly during the intervention, and after the intervention;
- a broad measure anxiety and potential generalization of treatment to other anxiety domains, the Multidimensional Anxiety Scale for Children 2nd Edition (MASC-2);
- social skills by administering the Social Skills Questionnaire (SSQ) ;
- social functioning using the Adolescent Social Self-Efficacy Scale (ASSES).

The criterion for statistical significance is $p < 0.05$. Results with $p < 0.1$ will be described as trends.

The primary analysis time point is the post-intervention assessment.

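### The SAP names the SPAI-B where the protocol specifies the SPAI at V1 and V3, so the form and baseline of this secondary outcome are undefined

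*SAP*

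**What the plan says.** The SAP, section (2), lists five secondary outcomes. The self-report one is "self-report inventories of social anxiety symptoms through the Social Phobia and Anxiety Inventory-Brief (SPAI-B"), with collection at baseline, every week of the intervention and afterwards. No arm is specified for the weekly collection, and the SPAI is not in the list.

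The protocol, under Anxiety and Social Anxiety, has "Self-report inventories of social anxiety symptoms through the Social Phobia and Anxiety Inventory (SPAI"), which "will be completed at the *Baseline* (V1) and *End of Study* (V3"). Its secondary outcome paragraph, at the end of Intervention Embedded Assessments, and its Data Analysis section both give "self-report inventories of social anxiety symptoms (SPAI"). Appendix I has one row for the "Social Phobia and Anxiety Inventory-Brief version", marked at screening only, and a separate row for the SPAI, marked at V1 and V3.

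The protocol gives the SPAI-B other jobs:

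- Inclusion criterion 3 requires a score of at least 25.
- Under WASABI Alerts, when social anxiety is detected from EMA metrics, "cognitive biases assessments, and the Social Phobia and Anxiety Inventory-Brief (SPAI-B), the monitoring clinician will receive an alert".
- Under Intervention Embedded Assessments, those assigned to "receive WASABI will also complete a weekly SPAI-B assessment".
- Its completion rate is one of the primary feasibility outcomes.

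Under Active Control Program, control participants complete two embedded sessions that include the SPAI-B, one before and one after the 12 weeks. The pre-intervention session is at V2, where both arms "complete a series of mobile assessments during this visit (embedded baseline assessments via BrainHQ"). Study Procedures places V2 after the randomization step.

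**The concern.** A reader cannot tell from the two documents which scale carries the secondary self-report result. If the scales are distinct, the SAP has replaced an instrument given on the same schedule in both arms with one that is part of the experimental intervention. The SPAI-B is answered far more often in one arm, it triggers clinician contact in that arm, and the un-blinded clinician can read the scores in the web portal (Application Security, BrainHQ). The SAP also says that blinded, trained staff collected the secondary outcomes. That does not describe a questionnaire self-completed in the BrainHQ app.

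The SAP puts its emphasis on a standardised effect size rather than on p-values, and the protocol says the trial data will be used to power a pivotal study. With two possible instruments, and two possible baselines for one of them, several effect sizes could be reported for the same construct, and nothing in the plan fixes the choice.

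**Working it through.** There is no planned figure to reproduce. The check is a comparison of the texts, a count of administrations and a look at the available baselines.

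**1. Instrument and timing**

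| Place | Instrument | Timing |
|---|---|---|
| Protocol, Anxiety and Social Anxiety | SPAI | V1, V3 |
| Protocol, secondary outcomes | SPAI | none given |
| Protocol, Data Analysis | SPAI | none given |
| Appendix I, first row | SPAI-B | screening |
| Appendix I, second row | SPAI | V1, V3 |
| SAP (2), secondary outcomes | SPAI-B | baseline, weekly, post |

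Appendix I covers only screening, V1 and V3, so it does not show the embedded sessions.

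**2. Scheduled SPAI-B administrations per participant**

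- WASABI: 1 screening + 1 pre + 12 weekly + 1 post = 15. This falls to 14 or 13 if a weekly administration doubles as the pre score, the post score or both.
- Control: 1 screening + 1 pre + 1 post = 3.
- Difference at the maximum: 15 − 3 = 12, the weekly series.
- If the V1 and V3 scale is itself the brief form, given separately from the embedded sessions, both counts rise by 2, to 17 and 5. The difference is still 12.

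**3. Available SPAI-B baselines, if the SPAI is a distinct scale**

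- The screening score: before randomization, but selected to be at least 25.
- The embedded V2 score: before the intervention starts, but after randomization.

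No third one is scheduled, and the SAP says only baseline. If the V1 form is the brief one, V1 supplies an unselected occasion before randomization and this difficulty goes away.

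**4. Why the choice of baseline is not neutral**

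The SAP's effect size is d = (change in WASABI − change in control) / pooled baseline SD. A cut at 25 removes low scores, so an SD computed on screening scores is smaller than in the unselected population, and d is larger for the same raw difference.

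The documents give no SPAI-B mean or SD, so the following is illustration only. It assumes normal scores before selection, truncated to 25–80, with an SD of 8 to 12. The inflation factor is the unselected SD divided by the truncated SD:

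- pre-selection mean 50: 1.01 to 1.08
- mean 35: 1.19 to 1.31 (for SD 10, 10 / 7.93 = 1.26)
- mean 25: 1.66

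These factors are relative to an unselected SD. V2 scores come from the same selected participants and would be partly restricted too, so the gap between the screening and V2 standardisers would be smaller.

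**The case against.** **SPAI may simply be shorthand for SPAI-B.** The paper cited for the SPAI (reference 51) is the one on the brief form for adolescents, and the list under Surveys, Questionnaires and Other Data Collection Instruments has the SPAI-B but no separate SPAI. The SAP may then be naming the instrument correctly. This stands as a real possibility, so a reader should not conclude that the SAP is the document in error. Against it, the protocol puts SPAI-B completion among the primary outcomes and the SPAI among the secondary ones in consecutive paragraphs, and Appendix I separates the two by row and visit. On either reading at least one document needs correcting.

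**Unequal data in the mixed model.** A reader might infer that weekly scores from one arm enter the between-arm comparison, or that control lacks endpoint data. The documents do not support either. The SAP describes growth models of change from baseline to post, defines its slope the same way, and makes post-intervention the primary time point. Both arms have pre and post scores. Weekly scores entering the model is a risk left open by loose wording and no more.

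**Regression to the mean.** A reader might infer that selection at 25 produces a large spurious improvement. No size can be supported. The effect arises only if the screening score is the baseline, which no passage says. Sixteen items scored 1 to 5 give a range of 16 to 80, so the cut lies 9 points above the floor, 9 / 64 = 14% of the range, and selection may be mild. Both arms are selected by the same rule before randomization, so the expected shift cancels in the SAP's between-arm d. It could affect only the protocol's within-group d.

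**A changed registered outcome.** Nothing can be said on this, since there is no registry record among the documents.

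**Importance.** The primary outcomes are feasibility measures, the protocol disclaims power for an augmentation effect, and the clinician-rated LSAS-CA is a separate social anxiety outcome that is untouched. This stands and limits the severity.

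**Conclusion.** The conflict is real and rests on the text alone: the protocol's outcome is the SPAI at V1 and V3, and the SAP's is the SPAI-B on a different schedule with an unspecified baseline. The asymmetry of up to 15 administrations against 3 follows from the protocol's schedule. It assumes that the WASABI arm's pre and post embedded sessions include the SPAI-B, as the control arm's do. No bias of known size has been shown, and which document is wrong cannot be settled from the texts. The point should be fixed before analysis, but it affects one of five secondary outcomes in an unpowered feasibility trial and does not threaten the primary outcomes.

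**What to change.** First establish which form is given at V1 and V3, and correct whichever document is wrong.

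- **If it is the full SPAI:** make the SPAI at V1 and V3 the secondary self-report outcome in the SAP. Keep the SPAI-B for screening, alerts and completion rate. Label any SPAI-B change as supportive, and state that its baseline is the V2 score, taken after randomization. Correct the citation and the instrument list.
- **If it is the brief form:** say so in both documents, including Appendix I, and use the V1 and V3 scores.
- **In either case:** state that only the pre and post scores common to both arms enter the between-arm model, and that weekly SPAI-B scores are feasibility or exploratory data from the WASABI arm. Limit the SAP's statement about blinded collection to the measures it fits.

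The cost is wording. The V1 and V3 scale is already scheduled in both arms, no new data are needed, and the weekly series keeps its feasibility use.
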